8.2.3 Exclusion criteria

- 1. Patients or physicians who previously participated in interventional programs for Saxenda[®] or Victoza[®] will not be eligible to participate in the study.
- 2. For the full study, sites and patients included in the pilot will be excluded.

8.2.4 Withdrawal criteria:

The patient may withdraw at will at any time.

8.2.5 Rationale for selection criteria

The selection of participating sites as well as the inclusion and exclusion criteria applied in this DUS allow for inclusion of a study population as broad as possible. Furthermore, the sampling strategy will be built so as to obtain a representative sample of physicians. Prescribers will be recruited according to setting characteristics, e.g., size of practice (small, medium, large), location (urban, rural), type (academic, non-academic) and reimbursement systems/patterns. In addition, prescribers who participated in interventional programs for Saxenda® or Victoza® will not be eligible to participate in the study. By applying this approach the representativeness and comprehensiveness of the sample in terms of types of prescribers and study population will ensure generalizability of study results to the broad population of subjects being prescribed Saxenda® or Victoza® in clinical practice. Furthermore, the exclusion criteria will limit potential bias related to awareness of the pilot study objectives and to extended knowledge on prescription of and use of Saxenda® and/or Victoza® (i.e., knowledge that goes beyond that obtained through normal clinical practice).

8.2.6 Flowchart

The data collection period for Saxenda[®]/Victoza[®] will be the interval between the launch date of Saxenda[®] to the index date of the pilot or full study, respectively. Table 1 and Table 2 show the data to be collected respectively for Saxenda[®] and Victoza[®] patients at different time points in relation to initiation of treatment. Data collection will encompass the following treatment periods for Saxenda[®]: (1) a time frame of 6 months prior to treatment initiation, (2) treatment initiation, (3) 4-12 weeks post treatment initiation, (4) 16-24 weeks post treatment initiation, and also (5) throughout the entire treatment period. Data collection will encompass the following treatment periods for Victoza[®]: (1) treatment initiation, and (2) throughout the entire treatment period.

Protocol	UTN: U1111-1185-3661	Date:	23 November 2015	Status:	Final	Novo Nordisk
Study ID: NN8022-4241	EU PAS No.:	Version:	5.0	Page:	23 of 53	

Table 1 - Saxenda® patients¹

Weeks in relation to initiation of treatment/time of first prescription	Prior to treatment initiation	0	4 – 12 weeks	16 – 24 weeks	Throughout the treatment period ²
Visit window			+4 weeks	+4 weeks	
Demography ³		X			
Co-morbidities ⁴	X				
Body Weight		X^5		X^6	
Adult height	X				
BMI		X^5			
Brand name		X			
Indication prescribed		X			
Target dose prescribed		X			
Current dose ⁷			X	X	
Treatment start date		X			
Treatment stop date					X
Concomitant medication with GLP-1					
receptor agonists					X
(Brand name and start date)					

- 1) Inclusion criteria must be fulfilled (incl. obtained informed consent) before data extraction is performed
- 2) Censoring at 24 months after launch
- 3) Sex, age
- 4) Diagnosis of or treatment of pre-diabetes, type 2 diabetes mellitus (T2DM), hypertension, dyslipidaemia and/or obstructive sleep apnoea.
- 5) Latest recording within 6 months before first prescription of Saxenda®
- 6) If not available the earliest subsequent body weight and date of measurement should be recorded
- 7) If treatment discontinuation occurs prior to/between the specified time points, the dose of Saxenda® at time of treatment discontinuation should be recorded.

Protocol		Date:	23 November 2015	Novo Nordisk
Study ID: NN8022-4241		Version:	5.0	
UTN: U1111-1185-3661		Status:	Final	
EU PAS No.:	CONFIDENTIAL	Page:	24 of 53	

Table 2 - Victoza® patients¹

Weeks in relation to initiation of treatment/time of first prescription	0	Throughout the treatment period ²
Demography ³	X	
Brand name	X	
Indication prescribed	X	
Target dose prescribed	X	
Dose-escalation of Victoza® 1.2 or 1.8 mg/day to Victoza® 3.0		X
mg/day		

¹⁾ Inclusion criteria must be fulfilled (incl. obtained informed consent) before data extraction is performed

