7.3 Endpoints

Primary endpoint:

The following endpoints will address the primary objective (concerning Saxenda® only):

BMI and comorbidities:

- Number of patients with Body Mass Index (BMI)≥30 kg/m² (measured less than 6 months before date of first prescription).
- Number of patients with 27 kg/m² ≤BMI<30 kg/m² (measured less than 6 months before date of first prescription) and
 - ≥1 relevant comorbidity registered:
 - Dysglycaemia (T2DM or prediabetes), hypertension, dyslipidaemia, and/or obstructive sleep apnoea.
 - o No relevant comorbidities (described above) registered.
- Number of patients with BMI<27 kg/m² (measured less than 6 months before date of first prescription).
- Number of patients with BMI not measured within 6 months before date of first prescription.

 Protocol
 Date:
 23 November 2015
 Novo Nordisk

 Study ID: NN8022-4241
 Version:
 5.0

 UTN: U1111-1185-3661
 Status:
 Final

 EU PAS No.:
 CONFIDENTIAL
 Page:
 17 of 53

Stopping rule:

- Number of patients with at least 5% weight loss (measured 16-24 weeks after first prescription date) and continuing treatment.
- Number of patients with less than 5% weight loss (measured 16-24 weeks after first prescription date) and continuing treatment.
- Mean weight loss (measured 16-24 weeks after first prescription date) in patients not treated according to stopping rule.

Secondary endpoint:

The following endpoint will be used to address the first secondary objective (concerning Victoza[®] only):

- Number of patients with Victoza[®] prescriptions fulfilling at least one of the following criteria:
 - 1. Dose information of 3.0 mg per day, or
 - 2. Indication of weight management.

The following endpoints will be used to address the second secondary objective (concerning Saxenda® only):

- Adherence to dose escalation according to label:
 - o Number of patients who have reached a dose of 3.0 mg within 4-12 weeks after first prescription date.
- Concomitant medication with of other GLP-1 receptor agonists:
 - Number of Saxenda[®] patients with other GLP-1 receptor agonists prescribed during continued treatment with Saxenda[®] (continued treatment is defined as no gaps between prescriptions of more than 90 days, identified by examining repeat prescription dates).
- Duration of treatment with Saxenda®:
 - o Number of patients with a treatment duration of:

Protocol		Date:	23 November 2015	Novo Nordisk
Study ID: NN8022-4241		Version:	5.0	
UTN: U1111-1185-3661		Status:	Final	

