8.3 Variables

Site characteristics:

To evaluate the representativeness of sites the following information will be collected for each participating site using a site questionnaire:

- Geographic location of physician site
- Specialty of participating physician (e.g., GPs, cardiologists, endocrinologists [or other diabetes and obesity specialists])
- Practice type (e.g., community hospital, academic/medical centre, office based)
- Practice size (number of physicians who practice at site)
- Patient volume (i.e., number of patients and estimated number of patients prescribed Saxenda[®] or Victoza[®]).

Additionally, the number of sites invited to participate within each specialty will be collected along with reason for refusal in order to evaluate the response rate and representativeness of the specialty. Sites and physicians will not be identifiable in the study report.

Patient demographics, medical history, and other characteristics:

- Date of birth
- Sex

Body weight (latest recording within 6 months before date of first prescription of Saxenda[®]), height, BMI (calculated), and date of anthropometric measurements (for Saxenda[®] patients only)

²⁾ Censoring at 24 months after launch

³⁾ Sex, age

 Protocol
 Date:
 23 November 2015
 Novo Nordisk

 Study ID: NN8022-4241
 Version:
 5.0

 UTN: U1111-1185-3661
 Status:
 Final

 EU PAS No.:
 CONFIDENTIAL
 Page:
 25 of 53

Drug utilisation:

Saxenda[®] or Victoza[®] patients:

- Brand name
- Indication prescribed at treatment initiation
- Target dose prescribed at treatment initiation
- Repeat prescription dates

Saxenda® patients only:

- Treatment start date and end date
- Comorbidities:
 - Dysglycaemia (T2DM or prediabetes), hypertension, dyslipidaemia, and/or obstructive sleep apnoea, before first prescription date. Diagnosis of dysglycaemia or dyslipidaemia may be based on relevant concomitant glucose lowering therapy (ATC code A10) or lipid lowering therapy (ATC code C10), respectively. In addition, diagnosis of dysglycaemia may be in the form of a relevant glycated haemoglobin (HbA1c), Oral Glucose Tolerance Test (OGTT) or fasting plasma glucose (FPG) measurement. According to the American Diabetes Association (ADA), prediabetes and diabetes may be defined based on the following laboratory cut-off values (4):

Prediabetes:

- FPG > 100 mg/dL (5.6 mmol/L) and < 125 mg/dL (6.9 mmol/L) and/or
- 2 hour post-challenge (OGTT) plasma glucose ≥ 140 mg/dL (7.8 mmol/L) and ≤ 199 mg/dL (11.0 mmol/L) and/or

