- HbA1c 5.7-6.4% (both inclusive)

T2DM:

- FPG \geq 126 mg/dL (7.0 mmol/L) and/or
- 2 hour post-challenge (during an OGTT) plasma glucose ≥ 200 mg/dL (11.1 mmol/L) and/or
- HbA1c > 6.5%
- O Diagnosis of obstructive sleep apnoea may be based on treatment with continuous positive airway pressure (CPAP) device.
- Concomitant medication with other GLP-1 receptor agonists (brand name and start date).
- Dose at 4-12 weeks and 16-24 weeks post initiation of treatment
- Body weight at 16-24 weeks post initiation of treatment. If body weight is not available within this interval, the earliest subsequent body weight and date of measurement should be recorded

Victoza® initators only:

• Dose throughout the treatment period

 Protocol
 Date:
 23 November 2015
 Novo Nordisk

 Study ID: NN8022-4241
 Version:
 5.0

 UTN: U1111-1185-3661
 Status:
 Final

 EU PAS No.:
 Page:
 26 of 53

Prescription outside label

Prescription outside label will be categorised as follows:

Saxenda® patients:

- BMI<27 kg/m² within 6 months before date of first prescription
- 27 kg/m² ≤BMI < 30 kg/m² within 6 months before date of first prescription and no relevant comorbidities registered (dysglycaemia [T2DM or prediabetes], hypertension, dyslipidaemia, and/or obstructive sleep apnoea)
- BMI not measured within 6 months before date of first prescription
- Non-adherence to dose escalation according to SmPC (i.e., daily dose of 3.0 mg not reached within 4-12 weeks post initiation of treatment)
- Non-adherence to stopping rule (i.e., less than 5% weight loss after 16-24 weeks on Saxenda[®] 3.0 mg and still on continued treatment)
- Concomitant medication with other GLP-1 receptor agonists

Victoza® patients:

- Dose of 3.0 mg per day
- Prescribed indication of weight management

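### At BMI 27 to <30, Table 1 footnote 4, the 8.2.6 period list and section 8.3 do not give one consistent comorbidity definition, and the narrower readings count some on-label Saxenda patients as outside label

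*Protocol*

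**What the plan says.** **Evidence.** In section 8.2.6, Table 1 footnote 4 defines the co-morbidity item as "Diagnosis of or treatment of pre-diabetes, type 2 diabetes mellitus (T2DM), hypertension, dyslipidaemia and/or obstructive sleep apnoea". Section 8.3 then goes condition by condition. For two of them, "Diagnosis of dysglycaemia or dyslipidaemia may be based on relevant concomitant glucose lowering therapy (ATC code A10) or lipid lowering therapy (ATC code C10), respectively". Dysglycaemia may also rest on an HbA1c, OGTT or FPG value, with cut-offs given. For sleep apnoea, "Diagnosis of obstructive sleep apnoea may be based on treatment with continuous positive airway pressure (CPAP) device". No corresponding sentence is given for hypertension.

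**Period.** The text of 8.2.6 lists five collection periods for Saxenda, the first being "a time frame of 6 months prior to treatment initiation". Table 1 has five columns in the same order, and co-morbidities are marked in the first, whose heading carries no time limit. Section 8.3 asks for dysglycaemia, "hypertension, dyslipidaemia, and/or obstructive sleep apnoea, before first prescription date", again without a lower limit. Footnote 5 ties a 6-month limit to weight and BMI: "Latest recording within 6 months before first prescription of Saxenda".

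**Use.** Section 7.3 splits the BMI 27 to <30 group in the primary endpoint into patients with at least one relevant comorbidity and those with "No relevant comorbidities (described above) registered". Section 8.3 puts the second group in the outside-label list, and section 8.7.2 names the proportion of prescriptions outside label as the main analysis.

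**The concern.** An abstractor needs two facts for each condition: what evidence counts, and how far back to look. On both, the places that should answer do not match. Someone working from the condition list in 8.3 has no stated route for a patient who takes antihypertensives but has no written diagnosis. Someone working from footnote 4 alone has no stated route for prediabetes shown only by a laboratory value. Someone who applies the first 8.2.6 period to the first Table 1 column may disregard a chronic diagnosis last charted more than 6 months before the first prescription.

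In each case the narrower reading makes incomplete charting look like use outside the indication. Section 8.9 itself warns that these patients may be seen by several specialists and that a site may not have the full record. Abstraction is done by site staff or external abstractors in two countries, so a difference in reading could also pass for a difference in prescribing.

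The problem arises at collection. The only concomitant medication listed as a variable in its own right is other GLP-1 receptor agonists. Antihypertensive treatment would therefore reach the database only through the comorbidity item, and evidence that is never abstracted cannot be restored at analysis.

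**Working it through.** The protocol states no figure on this point, so the check is a comparison of the passages, followed by the arithmetic for one patient.

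**Step 1: accepted evidence, by condition**

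| Condition | Table 1 footnote 4 | Section 8.3 |
|---|---|---|
| Dysglycaemia | diagnosis or treatment; laboratory value not mentioned | A10 drugs, or HbA1c, OGTT or FPG value |
| Dyslipidaemia | diagnosis or treatment | C10 drugs |
| Sleep apnoea | diagnosis or treatment | CPAP |
| Hypertension | diagnosis or treatment | nothing stated |

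Neither source is simply a fuller version of the other. Footnote 4 is wider for hypertension, and 8.3 is wider for dysglycaemia.

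**Step 2: look-back**

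- The five 8.2.6 periods and the five Table 1 columns match in order: before initiation, initiation, 4-12 weeks, 16-24 weeks, throughout treatment.
- The only items marked in the first column are co-morbidities and adult height. Weight and BMI are marked in the second column (week 0), with their own limit in footnote 5.
- By position, then, the 6-month period falls on co-morbidities and height. By the wording of footnote 4, the column heading and 8.3, co-morbidities have no lower limit.

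**Step 3: three patients, each with BMI 28 and no other qualifying evidence**

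- *Antihypertensive therapy, no written diagnosis.* Footnote 4: on label. 8.3 list alone: no stated route, so outside label.
- *Sleep apnoea diagnosis charted only 2 years earlier.* 8.3: on label. 6-month period applied to the column: outside label.
- *HbA1c within 5.7-6.4%, no diagnosis, no drug.* 8.3: on label. Footnote 4 alone: no stated route, so outside label.

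**Step 4: weight of one patient**

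Section 8.2.1 plans 150 Saxenda patients in the full study, 75 per country.

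- Full study: 1/150 = 0.67 percentage points.
- One country: 1/75 = 1.33 percentage points.

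This takes all planned patients as the denominator. It applies directly to the proportion in this outside-label category. A combined outside-label proportion moves by the same amount only if the patient is not already outside label for another reason.

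**Step 5: number of patients**

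The total shift is 150 × (share at BMI 27 to <30) × (share of those whose status turns on the reading). The protocol gives neither share. If each is assumed to lie between 10% and 30%:

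- lowest: 150 × 0.10 × 0.10 = 1.5 patients, or 1 point;
- highest: 150 × 0.30 × 0.30 = 13.5 patients, or 9 points.

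This range only restates the assumptions and is not an estimate.

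**The case against.** The strongest reply is that the passages can be read together. Section 8.3 is permissive and says what a diagnosis may be based on. It neither demands a written diagnosis of hypertension nor excludes treatment. Footnote 4 can serve as the general rule, with 8.3 adding detail for three conditions. On timing, no sentence applies 6 months to comorbidities by name. Footnote 5 and the endpoint definitions attach it to weight and BMI, and a 6-month window makes little sense for adult height, which sits in the same column. The likely intent is that only weight and BMI are time-limited. Section 8.9 also promises completion guidelines with consistent instructions and training for all abstractors. Those guidelines and the SAP are not at hand and may settle the coding.

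Most of this stands. A reader might infer that the protocol states two opposing rules, that 8.3 rules out treated hypertension, or that the comorbidity look-back is fixed at 6 months. The text supports none of these: the first two read exclusion into silence, and the third rests only on matching a list to columns. A reader might also infer a shift of several percentage points, but that would rest wholly on assumed shares.

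The combined reading still has to be assembled by the reader. The laboratory route is absent from footnote 4, the hypertension route is absent from 8.3, and the 8.2.6 list points at a column that does not hold weight or BMI. Whoever writes the completion guidelines must resolve these points without a protocol text to follow.

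**Conclusion.** The concern holds as an inconsistency of definition. Footnote 4, the 8.2.6 period list and 8.3 do not together give one rule on which evidence counts and how far back to look. The error has one direction, since each narrower reading can only move a BMI 27 to <30 patient from on label to outside label. It affects part of a primary endpoint and the main analysis.

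Its overall size cannot be derived from the protocol. What can be stated is 0.67 points per reclassified patient in the full study and 1.33 within a country. The conclusion assumes that some abstraction follows a narrower passage as written and that documents not shown do not already resolve it. It is worth correcting before data collection because the remedy is nearly free and missing evidence cannot be recovered later.

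**What to change.** Reconcile 8.2.6, Table 1 and 8.3 into one data definition. A comorbidity counts if at least one of the following holds:

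- a diagnosis is recorded at any time up to the first prescription date;
- treatment for it is current at that date: A10 for dysglycaemia, C10 for dyslipidaemia, CPAP for sleep apnoea, antihypertensive therapy for hypertension;
- for dysglycaemia, a qualifying HbA1c, OGTT or FPG value is recorded at any time up to that date, using the laboratory route 8.3 already allows.

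State in 8.2.6 that the 6-month limit applies to weight and BMI only. Record for each comorbidity whether the evidence was a diagnosis, treatment or a laboratory value. Report the outside-label count with and without treatment-only cases.

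The cost is protocol and guideline wording, one CRF field and one extra table. The small downside is that some antihypertensives are prescribed for other reasons; the with/without table shows how far that matters. The change concerns data definition only and does not touch patient care.

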8.3 Variables

Site characteristics:

To evaluate the representativeness of sites the following information will be collected for each participating site using a site questionnaire:

- Geographic location of physician site
- Specialty of participating physician (e.g., GPs, cardiologists, endocrinologists [or other diabetes and obesity specialists])
- Practice type (e.g., community hospital, academic/medical centre, office based)
- Practice size (number of physicians who practice at site)
- Patient volume (i.e., number of patients and estimated number of patients prescribed Saxenda[®] or Victoza[®]).

Additionally, the number of sites invited to participate within each specialty will be collected along with reason for refusal in order to evaluate the response rate and representativeness of the specialty. Sites and physicians will not be identifiable in the study report.

Patient demographics, medical history, and other characteristics:

- Date of birth
- Sex

Body weight (latest recording within 6 months before date of first prescription of Saxenda[®]), height, BMI (calculated), and date of anthropometric measurements (for Saxenda[®] patients only)

²⁾ Censoring at 24 months after launch

³⁾ Sex, age

 Protocol
 Date:
 23 November 2015
 Novo Nordisk

 Study ID: NN8022-4241
 Version:
 5.0

 UTN: U1111-1185-3661
 Status:
 Final

 EU PAS No.:
 CONFIDENTIAL
 Page:
 25 of 53

Drug utilisation:

Saxenda[®] or Victoza[®] patients:

- Brand name
- Indication prescribed at treatment initiation
- Target dose prescribed at treatment initiation
- Repeat prescription dates

Saxenda® patients only:

- Treatment start date and end date
- Comorbidities:
 - Dysglycaemia (T2DM or prediabetes), hypertension, dyslipidaemia, and/or obstructive sleep apnoea, before first prescription date. Diagnosis of dysglycaemia or dyslipidaemia may be based on relevant concomitant glucose lowering therapy (ATC code A10) or lipid lowering therapy (ATC code C10), respectively. In addition, diagnosis of dysglycaemia may be in the form of a relevant glycated haemoglobin (HbA1c), Oral Glucose Tolerance Test (OGTT) or fasting plasma glucose (FPG) measurement. According to the American Diabetes Association (ADA), prediabetes and diabetes may be defined based on the following laboratory cut-off values (4):

Prediabetes:

- FPG > 100 mg/dL (5.6 mmol/L) and < 125 mg/dL (6.9 mmol/L) and/or
- 2 hour post-challenge (OGTT) plasma glucose ≥ 140 mg/dL (7.8 mmol/L) and ≤ 199 mg/dL (11.0 mmol/L) and/or
- HbA1c 5.7-6.4% (both inclusive)

T2DM:

- FPG \geq 126 mg/dL (7.0 mmol/L) and/or
- 2 hour post-challenge (during an OGTT) plasma glucose ≥ 200 mg/dL (11.1 mmol/L) and/or
- HbA1c > 6.5%
- O Diagnosis of obstructive sleep apnoea may be based on treatment with continuous positive airway pressure (CPAP) device.
- Concomitant medication with other GLP-1 receptor agonists (brand name and start date).
- Dose at 4-12 weeks and 16-24 weeks post initiation of treatment
- Body weight at 16-24 weeks post initiation of treatment. If body weight is not available within this interval, the earliest subsequent body weight and date of measurement should be recorded

Victoza® initators only:

• Dose throughout the treatment period

 Protocol
 Date:
 23 November 2015
 Novo Nordisk

 Study ID: NN8022-4241
 Version:
 5.0

 UTN: U1111-1185-3661
 Status:
 Final

 EU PAS No.:
 Page:
 26 of 53

Prescription outside label

Prescription outside label will be categorised as follows:

Saxenda® patients:

- BMI<27 kg/m² within 6 months before date of first prescription
- 27 kg/m² ≤BMI < 30 kg/m² within 6 months before date of first prescription and no relevant comorbidities registered (dysglycaemia [T2DM or prediabetes], hypertension, dyslipidaemia, and/or obstructive sleep apnoea)
- BMI not measured within 6 months before date of first prescription
- Non-adherence to dose escalation according to SmPC (i.e., daily dose of 3.0 mg not reached within 4-12 weeks post initiation of treatment)
- Non-adherence to stopping rule (i.e., less than 5% weight loss after 16-24 weeks on Saxenda[®] 3.0 mg and still on continued treatment)
- Concomitant medication with other GLP-1 receptor agonists

Victoza® patients:

- Dose of 3.0 mg per day
- Prescribed indication of weight management

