Protocol		Date:	23 November 2015	Novo Nordisk
Study ID: NN8022-4241		Version:	5.0	
UTN: U1111-1185-3661		Status:	Final	
FILPAS No:	CONFIDENTIAL	Page.	1 of 53	

Protocol

Study ID: NN8022-4241

In-market utilisation of liraglutide used for weight management in Europe: a retrospective medical record review study

Redacted protocol Includes redaction of personal identifiable information only.

Non-interventional study

(1) Novo Nordisk – Epidemiology;	

Protocol originator:-

This confidential document is the property of Novo Nordisk. No unpublished information contained herein may be disclosed without prior written approval from Novo Nordisk. Access to this document must be restricted to relevant parties.

Protocol		Date:	23 November 2015	Novo Nordisk
Study ID: NN8022-4241		Version:	5.0	
UTN: U1111-1185-3661		Status:	Final	
EU PAS No.:	CONFIDENTIAL	Page:	2 of 53	

PASS information

1 ASS IIIUI IIIatiuii	
Title	In-market utilisation of liraglutide used for weight management in Europe: a retrospective medical record review study
Protocol version identifier	5.0
Date of last version of protocol	23 November 2015
EU PAS Register number	Study to be registered
Active substance	Liraglutide (ATC code: A10BX07)
Medicinal product	Saxenda [®] Victoza [®]
Product reference	
Procedure number	
Marketing authorisation holder(s)	Novo Nordisk
Joint Post Authorisation Safety Study (PASS)	No
Research question and objectives	To investigate in-market utilisation of liraglutide used for weight management: • Use of Saxenda® according to approved indication. • Use of Victoza® for weight management. • Use of Saxenda® according to approved posology.
Country(-ies) of study	Two European Union (EU) countries
Author	

Marketing authorisation holder(s)

Marketing authorisation holder (s) (MAH (s))	Novo Nordisk [name]
MAH contact person	

CONFIDENTIAL

23 November 2015 | Novo Nordisk Date: 5.0 Final Version: Status: 3 of 53 Page:

Table of Contents

				Page
Ma	arketin	g authoris	sation holder(s)	2
Ta	ble of (Contents		3
1	List o	of abbrevia	ations	5
2			rties	
	•	-		
3				
	3.1		11111	
	3.2 3.3		le and background	
	3.3 3.4		th question and objectives	
	3.4	-	esign	
	3.6		iones	
	3.7		ize	
	3.8	•	alysis	
			, and the second	
4			nd updates	
5	Miles	tones		14
6	Ratio	nale and b	background	14
7	Resea	arch quest	ion and objectives	15
	7.1	Primary	objective	15
	7.2	Seconda	ary objective(s)	16
	7.3	Endpoir	nts	16
8	Resea	arch meth	ods	18
	8.1	Study d	esign	18

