been shown to reduce hyperglycaemia in patients with type 2 diabetes mellitus (T2DM). The mechanisms of action for liraglutide include stimulation of insulin secretion and decrease of glucagon secretion, both in a physiological and glucose dependent-manner. The effects of liraglutide also include reduced sensation of hunger and increased satiety, leading to decreased food intake and subsequent weight loss.

Victoza[®] is indicated for the treatment of adults with T2DM at doses of 1.2 mg and 1.8 mg, and received marketing authorisation from the European Medicines Agency (EMA) in June 2009. Saxenda[®] (liraglutide 3.0 mg) is indicated as an adjunct to a reduced-calorie diet and increased physical activity for weight management in adults who are obese, or adults who are overweight with at least one weight-related comorbidity. The efficacy of Saxenda[®] was demonstrated in five phase 2 and 3 clinical trials involving around 5,800 obese/overweight patients, which showed that more patients administered Saxenda[®] achieved clinically relevant weight loss than those treated with placebo. Saxenda[®] received marketing authorisation from the EMA in March 2015.

As defined in the Risk Management Plan (RMP) for Saxenda[®], a retrospective drug utilisation study (DUS) to investigate patterns of use of Saxenda[®] and Victoza[®] in routine clinical practice has been requested by the EMA as a post marketing requirement. As is the case with any medicinal product, real-world use of Saxenda[®] or Victoza[®] may differ from the approved indication or recommendations outlined in the Summary of Product Characteristics (SmPC) (1, 2). Considering that these two liraglutide products with the same strength and formulation will be available for different indications with different doses, there is the potential for inadvertent use of one or the other product for either indication. The DUS will allow assessment of usage patterns of liraglutide for weight management, and thereby could refine pharmacovigilance planning and risk management.

7 Research question and objectives

The aim of this study is to investigate in-market utilisation of liraglutide for weight management. Specifically, the primary and secondary objectives are the following:

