8.2.2 Inclusion criteria

To be eligible for the study, patients will be required to meet both of the following inclusion criteria:

1. Initiation of Saxenda® or Victoza® (initiation is defined as no prescription of the same brand within the previous 12 months).

Protocol		Date:	23 November 2015	Novo Nordisk
Study ID: NN8022-4241		Version:	5.0	
UTN: U1111-1185-3661		Status:	Final	
EU PAS No.:	CONFIDENTIAL	Page:	22 of 53	

2. Informed consent obtained before any study-related activities. Study-related activities (e.g. data collection) are any procedures that are carried out as part of the study, including activities to determine suitability of the study.

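### The A10 drug route to dysglycaemia does not exclude earlier liraglutide, so Victoza given for weight can make a later Saxenda prescription at BMI 27 to <30 count as on-label

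*Protocol*

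**What the plan says.** Protocol section 8.3 lists the comorbidities that matter for label status as dysglycaemia, "hypertension, dyslipidaemia, and/or obstructive sleep apnoea, before first prescription date". It then gives a drug-based route: "Diagnosis of dysglycaemia or dyslipidaemia may be based on relevant concomitant glucose lowering therapy (ATC code A10) or lipid lowering therapy". It does not define which therapy is relevant and excludes no agent.

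Four other places bear on this rule.

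- The PASS information table gives the active substance as "Liraglutide (ATC code: A10BX07", so liraglutide lies inside A10.
- Section 8.2.2 defines new use by brand: "initiation is defined as no prescription of the same brand within the previous 12 months".
- Section 6 gives cross-use of the two brands as a reason for the study: "there is the potential for inadvertent use of one or the other product for either indication".
- Table 1 (section 8.2.6) marks comorbidities only before treatment initiation, and its footnote 4 describes them as diagnosed or treated conditions. It collects the brand and start date of GLP-1 receptor agonists only during the Saxenda treatment period.

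For the laboratory route, section 8.3 says that "prediabetes and diabetes may be defined based on the following laboratory cut-off values". The prediabetes ranges include "HbA1c 5.7-6.4% (both inclusive" and "FPG > 100 mg/dL (5.6 mmol/L) and < 125 mg/dL (6.9 mmol/L) and/or". T2DM is printed as HbA1c above 6.5% and FPG of at least 126 mg/dL.

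**The concern.** In the band 27 ≤ BMI < 30, one registered comorbidity separates an on-label from an off-label Saxenda prescription. The group in that band without a comorbidity is a primary-endpoint category (section 7.3). It also feeds the main analysis in section 8.7.2, the proportion of prescriptions outside label.

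The drug-based route treats glucose-lowering therapy as a sign of a glucose disorder. That inference is weak for liraglutide, because the protocol expects that some of its use as Victoza is for weight. Where that happened before Saxenda, the proxy can turn one off-label prescription into the justification for the next. The error runs in one direction, towards apparent compliance with the label.

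The listed data items would not let a later analysis undo the error. For Saxenda patients, neither Table 1 nor section 8.3 asks for the brand, dates or indication of a Victoza course that ended before Saxenda began. Such a course would surface only as a registered comorbidity. The rule therefore needs to be right before abstraction starts.

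**Working it through.** No sample-size or test figure is involved, because the study is descriptive. The check is of a classification rule.

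**Step 1: can prior Victoza satisfy the rule?**
1. The proxy is glucose-lowering therapy in ATC group A10 (section 8.3).
2. Liraglutide is A10BX07 (PASS information), so it is in the group.
3. No clause removes liraglutide or other GLP-1 receptor agonists.
4. The new-user rule looks back 12 months for the same brand only (section 8.2.2), so earlier Victoza does not bar entry as a Saxenda initiator.
5. A patient with BMI 27 to <30, Victoza prescribed for weight, then Saxenda, and no hypertension, dyslipidaemia or sleep apnoea can be recorded as dysglycaemic. That patient moves from the no-comorbidity category to the on-label one.

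The word concomitant sits uneasily with the limit to the time before first prescription. The protocol does not say whether the A10 drug must still be in use when Saxenda starts. A patient switched directly from one brand to the other could be read either way.

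**Step 2: weight of one patient.** Section 8.2.1 plans 150 Saxenda patients in the full study, 75 per country. With these as denominators:
- full study: 1/150 = 0.67 percentage points
- one country: 1/75 = 1.33 percentage points

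**Step 3: illustration only.** The protocol gives no rates. Assume that a share s of Saxenda patients, 10% to 30%, has BMI 27 to <30, and that a share r of those, 5% to 20%, changes label status through the rule. The number moved is 150 × s × r:
- low: 150 × 0.10 × 0.05 = 0.75 patients, or 0.5 points
- high: 150 × 0.30 × 0.20 = 9 patients, or 6 points

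Both shares are assumptions, so this range is not an estimate.

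**Step 4: laboratory ranges as printed.**

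| Measure | Prediabetes | T2DM | Values in no class |
|---|---|---|---|
| HbA1c, % | 5.7 to 6.4 inclusive | >6.5 | 6.5 |
| FPG, mg/dL | >100 and <125 | ≥126 | 100, 125 |
| FPG, mmol/L | >5.6 and <6.9 | ≥7.0 | 5.6, 6.9 |
| OGTT, mg/dL | 140 to 199 inclusive | ≥200 | none |

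The check ran in steps of 0.1% for HbA1c, 1 mg/dL and 0.1 mmol/L, from the prediabetes lower limit upward. With inclusive limits (HbA1c ≥6.5% as T2DM; FPG 100 to 125 mg/dL, or 5.6 to 6.9 mmol/L, as prediabetes) no value is left unclassified. These gaps act in the opposite direction to the drug route: they can leave a dysglycaemic patient without a registered comorbidity.

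**The case against.** The strongest defence is that the wording is permissive and qualified: dysglycaemia may be based on relevant therapy. Footnote 4 to Table 1 speaks of treatment of prediabetes or T2DM, and Victoza given for weight is not that. Victoza's indication is T2DM (section 6), so in labelled use it is a fair marker of the disease. A recorded diagnosis or any of the three other comorbidities also suffices, which leaves a narrow group. CRF completion guidelines are planned (section 8.9) and could define which therapy is relevant.

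Much of this stands, and it limits the size of the point. It does not remove the defect. Footnote 4 does not tell an abstractor how to recognise treatment of dysglycaemia; section 8.3 does, and it does so by the A10 code. Nor do the other outside-label categories repair the primary one. The GLP-1 category covers agents prescribed during continued Saxenda treatment, so it misses a course that had ended. The Victoza weight-management endpoint concerns Victoza patients only and does not reclassify Saxenda patients.

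Three stronger readings are tempting, and the document does not support them.

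- A reader might infer that Saxenda itself, being liraglutide, proves dysglycaemia in every Saxenda patient, so that the no-comorbidity category is empty by construction. Section 8.3 limits comorbidities to the time before first prescription and Table 1 marks them only before initiation, so the index prescription should not count.
- A reader might infer that any A10 drug qualifies and that every switcher from Victoza is on-label by definition. The permissive and qualifying words and footnote 4 rule that out; the patient can be so classified, not must be.
- A reader might take the laboratory gaps as an established error. They rest on strict against inclusive signs in machine-read text, and such signs are not reliable here: the upper BMI limit of the indication appears as ≤30 in section 3.3 and <30 in section 7.1. The adjacent OGTT limits are inclusive and contiguous, which suggests that inclusive signs may have been meant throughout.

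**Conclusion.** The point holds in narrow form. The A10 route does not exclude prior liraglutide or other GLP-1 receptor agonists and does not define relevant therapy. It can therefore place a patient inside the label on the strength of earlier Victoza use for weight. This biases a primary-endpoint category towards label compliance.

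How many patients are affected is unknown. They would need BMI 27 to <30, a GLP-1 agonist given for weight before Saxenda, none of the other three comorbidities, and neither a dysglycaemia diagnosis nor a qualifying laboratory value. The per-patient weights shown above assume that the planned 150 and 75 Saxenda patients are the denominators.

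The laboratory gaps are secondary and conditional on the source page. The rule should be corrected before abstraction; it does not threaten the study as a whole.

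**What to change.** In section 8.3 and the CRF completion guideline:

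1. Accept A10 therapy as proof of dysglycaemia only if it was started before the first Saxenda prescription, and state this in place of the undefined terms relevant and concomitant.
2. Do not accept liraglutide or another GLP-1 receptor agonist alone. Require that the record also shows T2DM or prediabetes as its indication, a diagnosis, or a qualifying laboratory value.
3. Check the inequality signs on the source page. If they are as printed, make the HbA1c and FPG ranges contiguous, so that every value from the prediabetes lower limit upward falls in exactly one class.

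The cost is a few lines of wording and abstractor training. The downside is that a few patients with true diabetes, treated only with a GLP-1 receptor agonist and with none of these records, would be counted as dysglycaemia-free. Those in the BMI band without another comorbidity would then be counted as off-label. Accepting the recorded indication as sufficient keeps that group small.
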